8.1.2 Laboratory test abnormalities

8.1.2.1 Definitions and reporting

Laboratory abnormalities that constitute an AE in their own right (are considered clinically significant, induce clinical signs or symptoms, require concomitant therapy or require changes in study treatment), should be recorded on the Adverse Events eCRF. Whenever possible, a diagnosis, rather than a symptom should be provided (e.g. anemia instead of low hemoglobin). Laboratory abnormalities that meet the criteria for AEs should be followed until they have returned to normal or an adequate explanation of the abnormality is found. When an abnormal laboratory or test result corresponds to a sign/symptom of an already reported adverse event, it is not necessary to separately record the lab/test result as an additional event.

Laboratory abnormalities that do not meet the definition of an AE should not be reported as AEs. A Grade 3 or 4 event (severe) as per CTCAE does not automatically indicate an SAE unless it meets the definition of seriousness below and/or at the investigator's discretion. A dose hold or medication for the laboratory abnormality may be required by the protocol in which case the laboratory abnormality would, by definition, be an AE and must be reported as such (see [Section 6.2](#)).

8.1.3 Adverse events of special interest

Adverse events of special interest to be monitored for LDK378 have also been identified and include: hepatotoxicity, interstitial lung disease/pneumonitis, QT interval prolongation, bradycardia, hyperglycemia gastrointestinal toxicity (nausea, vomiting and diarrhea) and pancreatitis (including lipase and amylase elevations).

Details regarding these adverse events are provided in the Investigator's Brochure for LDK378. Potential emergent new AEs will be monitored during the course of the study.

8.2 Serious adverse events

8.2.1 Definitions

An SAE is defined an AE characterized by one of the following:

- Is fatal or life-threatening
- Results in persistent or significant disability/incapacity
- Constitutes a congenital anomaly/birth defect
- Is medically significant, i.e., defined as an event that jeopardizes the patient or may require medical or surgical intervention to prevent one of the outcomes listed above
- Requires inpatient hospitalization or prolongation of existing hospitalization,
- Note that hospitalizations for the following reasons should not be reported as serious adverse events:
 - Routine treatment or monitoring of the studied indication, not associated with any deterioration in condition
 - Elective or pre-planned treatment for a pre-existing condition that is unrelated to the indication under study and has not worsened since signing the informed consent
 - Social reasons and respite care in the absence of any deterioration in the patient's general condition
- Note that treatment on an emergency outpatient basis that does not result in hospital admission and involves an event not fulfilling any of the definitions of a SAE given above is not a serious adverse event
- Protocol exempt SAEs: Progression of malignancy (including fatal outcomes), if documented by use of appropriate method (RECIST criteria), should not be reported as a serious adverse event.

8.2.2 Reporting

To ensure patient safety, every SAE, regardless of suspected causality, occurring after the patient has provided informed consent and until at least 30 days after the patient has stopped study treatment must be reported to Novartis within 24 hours of learning of its occurrence.

Any SAE experienced after this 30 days period should only be reported to Novartis if the investigator suspects a causal relationship to the study treatment. Recurrent episodes, complications, or progression of the initial SAE must be reported as follow-up to the original episode within 24 hours of the investigator receiving the follow-up information. An SAE

occurring at a different time interval or otherwise considered completely unrelated to a previously reported one should be reported separately as a new event.

Information about all SAEs is collected and recorded on the Serious Adverse Event Report Form; all applicable sections of the form must be completed in order to provide a clinically thorough report. The investigator must assess and record the relationship of each SAE to each specific study treatment (if there is more than one study treatment), complete the SAE Report Form in English, and submit the completed form within 24 hours to Novartis. Detailed instructions regarding the SAE submission process and requirements for signatures are to be found in the investigator folder provided to each site. Follow-up information is submitted in the same way as the original SAE Report. Each re-occurrence, complication, or progression of the original event should be reported as a follow-up to that event regardless of when it occurs. The follow-up information should describe whether the event has resolved or continues, if and how it was treated, whether the blind was broken or not, and whether the patient continued or withdrew from study participation.

If the SAE is not previously documented in the Investigator's Brochure or Package Insert (new occurrence) and is thought to be related to the Novartis study treatment, an oncology Novartis DS&E department associate may urgently require further information from the investigator for Health Authority reporting. Novartis may need to issue an Investigator Notification (IN), to inform all investigators involved in any study with the same drug that this SAE has been reported. Suspected Unexpected Serious Adverse Reactions (SUSARs) will be collected and reported to the competent authorities and relevant ethics committees (EC) in accordance with Directive 2001/20/EC or as per national regulatory requirements in participating countries.

8.3 Emergency unblinding of treatment assignment

Not applicable. This is an open-label study.

8.4 Pregnancies

[figure not shown]
Patients who become pregnant during the trial will be withdrawn from the study.

To ensure patient safety, each pregnancy occurring while the patient is on study treatment must be reported to Novartis within 24 hours of learning of its occurrence. The pregnancy should be followed until 3 months following delivery to determine outcome, including spontaneous or voluntary termination, details of the birth, and the presence or absence of any birth defects, congenital abnormalities, or maternal and/or newborn complications.

Pregnancy should be recorded on a Clinical Trial Pregnancy Form and reported by the investigator to the oncology Novartis DS&E. Pregnancy follow-up should be recorded on the same form and should include an assessment of the possible relationship to the investigational treatment of any pregnancy outcome. Any SAE experienced during pregnancy must be reported on the SAE Report Form.

8.5 Warnings and precautions

No evidence available at the time of the approval of this study protocol indicated that special warnings or precautions were appropriate, other than those noted in the provided Investigator

Brochure. Additional safety information collected between IB updates will be communicated in the form of Investigator Notifications. This information will be included in the patient informed consent and should be discussed with the patient during the study as needed.

8.6 Data Monitoring Committee (DMC)

An independent Data Monitoring Committee (DMC) will be constituted and will be responsible for monitoring and reviewing the clinical study data for efficacy and safety during the study prior to the final data analysis. Efficacy data will be reviewed periodically during Stage 1 to advise on whether the trial should proceed to Stage 2 and full enrolment. DMC review for the purpose of advising on the transition of the trial from Stage 1 to Stage 2 will be based primarily on local investigator assessment of response. However, the DMC may request data on assessment of response by the BIRC if deemed necessary. Responsibilities of the DMC, communication flow between DMC, Steering Committee and Novartis, and timing of data safety and efficacy reviews, will be included in the DMC charter document.

It is envisioned that the DMC may make four types of recommendations, namely:

[figure not shown]
[figure not shown]
1. Transition into Stage 2 of the trial or stopping enrollment after stage 1 for futility
2. No safety or ethical issues, ethical to continue the trial as planned
3. Serious safety concerns precluding further study treatment, regardless of efficacy
4. Ethical to continue the study but recommend an amendment to the protocol (e.g. incorporate a safety analysis).

8.7 Steering Committee (SC)

A Steering Committee (SC), comprised of investigators in NSCLC management from the study, will be formed prior to initiation of the trial. The purpose of the SC is to provide overall guidance regarding design of the study, conduct and execution of the trial to include (but not limited to) safety, accrual and contribution to scientific input for publications.

Responsibilities of the SC and communication flow between DMC, SC and Novartis will be included in the SC charter document.

9 Data collection and management

[figure not shown]
[figure not shown]
[figure not shown]

9.2 Site monitoring

Before study initiation, at a site initiation visit or at an investigator's meeting, Novartis personnel (or designated CRO) will review the protocol and eCRFs with the investigators and their staff. During the study, the field monitor will visit the site regularly to check the completeness of patient records, the accuracy of entries on the eCRFs, adherence to the protocol and to Good Clinical Practice, the progress of enrollment, and to ensure that study treatment is being stored, dispensed, and accounted for according to specifications. Key study personnel must be available to assist the field monitor during these visits.

The investigator must maintain source documents for each patient in the study, consisting of case and visit notes (hospital or clinic medical records) containing demographic and medical information, laboratory data, electrocardiograms, and the results of any other tests or assessments. All information recorded on eCRFs must be traceable to source documents in the patient's file. The investigator must also keep the original signed informed consent form (a signed copy is given to the patient).

The investigator must give the monitor access to all relevant source documents to confirm their consistency with the eCRF entries. Novartis monitoring standards require full verification for the presence of informed consent, adherence to the inclusion/exclusion criteria and documentation of SAEs. Additional checks of the consistency of the source data with the eCRFs are performed according to the study-specific monitoring plan.

10 Statistical methods and data analysis

The data from all participating centers in this protocol will be combined. The primary analysis of study data will be conducted at the time when all patients have either completed at least six cycles of treatment or discontinued treatment. These data will be summarized in the primary Clinical Study Report (CSR). The final analysis of study data will be conducted at the end of the study (see Section 4.3). All available data from all patients up to this cutoff date will be analyzed. Additional data from patients continuing to receive study treatment after this time will be captured by a separate protocol. Efficacy and safety reports will be reviewed by a DMC regularly during the conduct of the study (see [Section 8.6](#) for details).

10.1 Analysis sets

10.1.1 Full Analysis Set

The Full Analysis Set (FAS) will include all patients who receive at least one dose of LDK378. Patients who are screened but never started treatment will be listed.

The FAS will be used for all listings of raw data. Unless otherwise specified the FAS will be the default analysis set used for all analyses, including the primary analysis.

[figure not shown]
10.1.2 Safety Set

The Safety Set will include all patients who receive at least one dose of LDK378.

10.1.3 Per-Protocol Set

The Per-Protocol Set (PPS) will consist of a subset of patients in the FAS who are compliant with requirements of the Clinical Study Protocol (CSP). The PPS will include patients who have an adequate tumor assessment at baseline, a follow-up tumor assessment >7 weeks after starting treatment (unless disease progression is observed before that time), and no major protocol deviations.

All major protocol deviations leading to exclusion from the PPS will be detailed in the Reporting and Analysis Plan (RAP).

10.2 Patient demographics/other baseline characteristics

Demographic and other baseline data including disease characteristics will be summarized descriptively for all patients for the FAS. Categorical data will be presented as frequencies and percentages. For continuous data, mean, standard deviation, median, 25th and 75th percentiles, minimum, and maximum will be presented.

10.3 Treatments (study treatment, concomitant therapies, compliance)

The actual dose and duration in days of LDK378 as well as the dose intensity (computed as the ratio of total dose received and actual duration) and the relative dose intensity (computed as the ratio of dose intensity and planned dose intensity), will be listed and summarized for all patients.

Dose reductions and dose interruptions (including the reasons for these) will be listed and summarized.

The safety set will be used.

Concomitant medications and significant non-drug therapies prior to and after the start of the study treatment will be summarized for all patients.

10.4 Primary objective

The primary objective is to evaluate the anti-tumor activity of LDK378.

10.4.1 Variable

[figure not shown]
The variable used to evaluate the anti-tumor activity of LDK378 is the overall response rate (ORR), defined as the proportion of patients with a best overall confirmed response of CR or PR, as assessed per RECIST 1.1 by the investigator ([Appendix II](#)).

10.4.2 Statistical hypothesis, model, and method of analysis

The primary analysis will be performed on the FAS.

The study targets an ORR of 50%. A response rate of 35% or less is considered as insufficient level of activity for the proposed patient population. Therefore, a null hypothesis of $ORR \leq 35\%$ vs. an alternative hypothesis of $ORR > 35\%$ will be tested using a one-sided test with alpha of 0.05 based on a Simon's optimal two-stage design ([Simon 1989](#)). If 45 or more responses are seen in 105 total patients (estimated ORR of 42.9%), then the null hypothesis will be rejected and the trial declared positive.

Stage 1 will enroll 43 patients. If the study is terminated early at the end of Stage 1 (16 or fewer responses among 43 patients enrolled to Stage 1), then the study will be considered to have failed to reject the null hypothesis. See [Section 10.7](#) for further details of the stopping

criteria for futility. Stage 2 will include an additional 62 patients. The primary analysis will occur when all 105 patients have completed 6 cycles of treatment or discontinued treatment earlier.

The ORR will be estimated and the 90% exact confidence interval (CI) will be provided. The uniformly minimum variance unbiased estimator (UMVUE) and the 90% two-stage CI (Atkinson and Brown 1985) will also be presented.

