Data analysis	
The cut-off date for the primary analysis of this trial will be the time when all 105 patients have completed 6 cycles of treatment or have discontinued treatment. The ORR per RECIST 1.1 by investigator assessment and by BIRC assessment will be estimated and the 90% confidence interval (CI) provided. If the true ORR is 50% (under the alternative hypothesis), approximately 105 patients are required to reject the null hypothesis of $ORR \leq 35\%$ with a one-sided alpha of 0.05 based on Simon's optimal two-stage design. If 45 or more responses are seen in 105 total patients (estimated ORR of 42.9%), then the null hypothesis will be rejected and the trial declared positive. If the study is terminated early at the end of Stage 1, then the study will be considered to have failed to reject the null hypothesis. The uniformly minimum variance unbiased estimator (UMVUE) and the 90% CI from Atkinson and Brown (1985) will also be presented.
 
DOR will be listed by patient and may be described using Kaplan-Meier methods and relevant statistics if appropriate. DCR and OIRR will be estimated and the 90% CI provided. TTR, PFS, and OS will be described using Kaplan-Meier methods and appropriate summary statistics.
 
Adverse events and laboratory abnormalities will be summarized and listed.

Key words	ALK, NSCLC, LDK378

Amendment 4

Amendment rationale

As of the release date of this amendment the recruitment has been completed and 132 patients have been screened to the study. A total of 124 patients have been treated.

This amendment has been implemented to:

- Update the protocol to include follow up evaluations for hepatic toxicities and work-up guidelines for potential Drug Induced Liver Injury (DILI) cases in order to optimize the patient safety.
- Update the dose guidance modification for QTcF text to provide clarification on monitoring procedure.
- Update the guidance related to corticosteroids use
- Update of the definition of the End of Study
- Editorial changes and text corrections were made for clarification, where required.

Changes to the protocol

Changes to specific sections of the protocol are shown in the track changes version of the protocol using strike through red font for deletions and red underlined font for insertions.

The following sections were changed:

- [List of abbreviations](#) updated with commonly used abbreviations such as R value, TBIL, DILI, EBV, CMV, and HSV

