The treatment period begins on Day 1 of Cycle 1. All patients will be treated with LDK378, administered orally, at a starting dose of 750 mg. A total of approximately 105 patients will be enrolled in the study. Patients will take LDK378 once daily, at approximately the same time each day.

Treatment with LDK378 will continue until the patient experiences unacceptable toxicity that precludes further treatment, discontinues treatment at the discretion of the patient or investigator, starts a new anti-cancer therapy or dies. If the patient experiences RECIST-defined progressive disease (PD) on LDK378 as

assessed by the investigator, treatment with the study drug may be continued if, in the judgment of the investigator, there is still evidence of clinical benefit. These patients will be counted as PD for ORR, DOR, DCR and PFS calculations.

Assessments of tumor response and progression will be performed every 8 weeks (i.e. every 2 cycles), starting from the first day of treatment with LDK378. This schedule of tumor assessment every 8 weeks must continue regardless of dose interruptions. Tumor assessment should continue until:

- For patients who experience PD as assessed by the investigator, tumor assessments should continue every 8 weeks until LDK378 is permanently discontinued (i.e. if the patient continues treatment with LDK378 after PD, tumor assessments should continue until LDK378 is permanently discontinued).
- For patients who discontinue treatment in the absence of PD, tumor assessments should continue every 8 weeks from the EOT visit until PD is assessed by the investigator.

Tumor evaluations will always cease if the patient withdraws consent (unless the patient agrees to continue efficacy assessments in absence of dosing with LDK378, see [Section 7.1.4.1](#)), or dies.

All tumor imaging assessments will be submitted for independent radiological assessment of response by a Blinded Independent Review Committee (BIRC).

Clinical and laboratory assessments will be performed as described in [Section 7](#).

When the patient discontinues from study treatment an End of Treatment (EOT) visit must be performed as soon as possible and within 7 days of the last dose of LDK378. Patients will be contacted for the safety follow-up 30 days after their last dose of LDK378 to determine if they have experienced any new AEs and/or to follow resolution of ongoing AEs.

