10.8 Sample size calculation

Based on [Simon's \(1989\)](#) optimal two-stage design, if the true ORR is 50% (under the alternative hypothesis), approximately 105 total patients are required to reject the null hypothesis of $ORR \leq 35\%$ with a one-sided alpha of 0.05 and 90% power. If at least 17 confirmed responses are observed among 43 patients enrolled into Stage 1, an additional 62 patients will be enrolled into Stage 2. If 45 or more confirmed responses are observed among 105 total patients, the trial will be declared positive.

The operating characteristics of the design are described in [Table 10-1](#).

Table 10-1 Operating characteristics of Simon's optimal two-stage design

	True ORR			
	35% (null hypothesis)	40%	45%	50% (alternative hypothesis)
Probability stop for futility at Stage 1 (16 or fewer responses out of 43 patients enrolled at Stage 1)	0.683	0.418	0.192	0.063
Probability trial is success (45 or more responses out of 105 total patients)	0.049	0.268	0.642	0.900

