### **Full Analysis Set**

The Full Analysis Set (FAS) consists of all patients who received at least one dose of study drug. All efficacy endpoints will be analyzed using FAS.

The FAS will be used for all listings. Unless otherwise specified the FAS will be the default analysis set used for all analyses.

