### **2.7.2 Statistical hypothesis model and method of analysis**

The primary efficacy analysis will be performed on the FAS.

The study targets an ORR of 50%. A response rate of 35% or less is considered as insufficient level of activity for the proposed patient population. Therefore,

$H_0: \text{ORR} \leq 35\%$  will be tested vs  $H_1: \text{ORR} > 50\%$

using a one-sided test with  $\alpha=0.05$  based on Simon's optimal two-stage design ([Simon 1989](#)). If 45 or more responses are seen in 105 total patients (estimated ORR of 42.9%), then  $H_0$  will be rejected and the trial declared positive.

Stage 1 will enroll 43 patients. If the study is terminated early at the end of Stage 1 (16 or fewer responses among 43 patients enrolled to Stage 1), then the study will be considered to have failed to reject  $H_0$ . See [Section 2.11](#) for further details of the stopping criteria for futility. Stage 2 will include an additional 62 patients. The primary analysis will occur when all 105 patients have completed 6 cycles of treatment or discontinued treatment earlier.

The ORR will be estimated and the 90% and 95% Clopper-Pearson (Clopper and Pearson 1934) confidence intervals (CIs) will be provided. The uniformly minimum variance unbiased estimator (UMVUE) and the 90% two-stage CI (Atkinson and Brown 1985) will also be presented. Refer to Section 4.6.4 for additional details.

Clopper-Pearson confidence intervals will be used since the confidence limits based on the normal approximation are not bounded by the  $[0, 1]$  interval, meaning that for rates close to 0 or 1, the upper limit of the normal approximation interval for the proportion could exceed 1 or the lower limit could be negative. The 90% two-stage CI will be presented to correspond to the Simon two-stage p-value.

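### The primary test is on the full analysis set (124 treated), but the success count, Stage 2 size and operating characteristics on record still describe 105 patients

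*Protocol*

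**What the plan says.** Protocol 10.4.2 and SAP 2.7.2 both place the primary efficacy analysis on the FAS. Protocol 10.1.1 defines that set: "The Full Analysis Set (FAS) will include all patients who receive at least one dose of LDK378". SAP 2.2 agrees: "The Full Analysis Set (FAS) consists of all patients who received at least one dose of study drug".

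Planned size, Protocol 4.1: "A total of approximately 105 patients will be enrolled in the study". Actual size, Amendment 4 rationale, which also says recruitment is complete: "A total of 124 patients have been treated".

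The decision rule in Protocol 10.4.2 is "If 45 or more responses are seen in 105 total patients (estimated ORR of 42.9%), then the null hypothesis will be rejected", and Protocol 10.8 repeats it: "If 45 or more confirmed responses are observed among 105 total patients, the trial will be declared positive". SAP 2.7.2 and 2.9 carry the same rule, with "Stage 2 will include an additional 62 patients". Protocol Table 10-1 and SAP Table 2-3 give operating characteristics for 105 patients only. SAP Table 3-1, which lists changes to protocol-specified analyses, has no entry for the larger sample.

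The SAP is dated 12 April 2018, after the final cut-off of 22 January 2018. It covers the final analysis. For the per-protocol definition it points to an earlier analysis plan (RAP Module 3 Amendment 1), which is not among the documents supplied.

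**The concern.** A Simon design fixes a success count for a fixed total. Here the analysis set is defined by dosing and contains 124 patients, while the count, the Stage 2 size, alpha and power were all worked out for 105. No passage restricts the test to the first 105 treated, and none says what happens if more are enrolled. For a result near the boundary, a reader cannot tell from these documents which count decided the trial.

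The estimates are affected too. The UMVUE, the two-stage confidence interval and any two-stage p-value depend on the stage sizes, so using 43 + 62 for a sample of 43 + 81 would give the wrong values. SAP section 2 is to be carried into the clinical study report, so the 105-patient description would go with it.

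**Working it through.** **Inputs.** Null ORR 0.35, target 0.50, one-sided alpha 0.05, power 90% (Protocol 10.4.2, 10.8). Stage 1: 43 patients, continue with 17 or more responses (10.7, 10.8). Stage 2: 62. Success: 45 of 105. Treated: 124, so 124 − 105 = 19 extra (18% above plan), and Stage 2 becomes 62 + 19 = 81.

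**Formula.** With b(x; 43, p) the binomial probability of x Stage 1 responses, n2 the Stage 2 size and r the success count,

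P(success) = Σ over x = 17 to 43 of b(x; 43, p) × P(Bin(n2, p) ≥ r − x).

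**Step 1: reproduce the plan.** With n2 = 62 and r = 45:

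| True ORR | 35% | 40% | 45% | 50% |
|---|---|---|---|---|
| Stop at Stage 1 | 0.6828 | 0.4178 | 0.1916 | 0.0631 |
| Success, 45 of 105 | 0.0487 | 0.2678 | 0.6418 | 0.9000 |

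All eight entries of Protocol Table 10-1 are recovered. The design is correct for 105.

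**Step 2: the FAS as treated.** With n2 = 81 and the Stage 1 rule unchanged (so the stopping probabilities are unchanged):

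| Success count | 35% (alpha) | 40% | 45% | 50% (power) |
|---|---|---|---|---|
| 52 of 124 | 0.0513 | 0.2994 | 0.6903 | 0.9195 |
| 53 of 124 | 0.0367 | 0.2520 | 0.6491 | 0.9092 |
| 54 of 124 | 0.0254 | 0.2065 | 0.6006 | 0.8943 |

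The smallest count with alpha at or below 0.05 is 53. Reading the stated 42.9% as a rate would instead require 54, because 53/124 = 42.7% and 54/124 = 43.5%.

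**Step 3: how often the choice matters.** Let S be the responses in the first 105, given that Stage 1 is passed, and Y ~ Bin(19, p) those in the last 19. The rules S ≥ 45 and S + Y ≥ 53 disagree with probability:

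| True ORR | 35% | 40% | 45% | 50% | 60% |
|---|---|---|---|---|---|
| Disagree | 0.0263 | 0.0830 | 0.0798 | 0.0251 | 0.0001 |

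The phase I crizotinib-naive response rate is 60% (21 of 35; Protocol 1.2.1.2.2, Table 1-2).

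**Step 4: the p-value.** SAP 2.7.2 says "The 90% two-stage CI will be presented to correspond to the Simon two-stage p-value", but SAP 4.6.4 programs only a single-stage exact binomial p-value against 0.35.

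| Result | Single-stage p | Two-stage p |
|---|---|---|
| 45 of 105 | 0.0579 | 0.0487 |
| 52 of 124 | 0.0650 | 0.0513 |
| 53 of 124 | 0.0448 | 0.0367 |

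At 124 patients both p-values first reach 0.05 or below at the same count, 53.

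**Step 5: estimation.** The UMVUE is 0.4508 at 45 of 105 (raw 0.4286) and 0.4523 at 53 of 124 (raw 0.4274). The correction to the raw rate is therefore 0.0222 in one case and 0.0249 in the other, which is why the actual stage sizes must be used.

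**The case against.** The strongest reply is that the decision may already have been settled elsewhere. This SAP covers the final analysis. The primary analysis had its own cut-off and report, and an earlier analysis plan exists. The SAP also carries older wording in places: its study-design section still requires prior chemotherapy, which the current protocol does not. Its repetition of 43 + 62 is therefore weak evidence that the 124 were never dealt with. This stands, and it limits the point to what the two supplied documents record.

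A second reply is that the planned size was only approximate and little changes. The counts of 53 and 54 keep alpha below 0.05 and power within about one point of 90%. That is also fair, and it keeps the severity low. But the success count and Stage 2 size are fixed integers, and 124 is 18% above 105.

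Three stronger readings are tempting and are not supported.

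- A reader might infer that 45 responses would be counted against all 124, giving alpha 0.222. Both documents tie the 45 to 105 patients, so that is not what they say.
- A reader might infer that SAP 4.6.4 contradicts the success rule, since 45 of 105 has a single-stage p of 0.058. No passage makes that p-value decisive, an analysis of 124 patients would not produce a 45-of-105 p-value, and even at 105 the clash covers one count (46 of 105 gives 0.038).
- A reader might treat 45 of the first 105 treated as the pre-specified test. Neither document defines such a set, and using it would take 19 dosed patients out of a test assigned to the FAS.

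**Conclusion.** The point holds in limited form. In the documents supplied, the threshold, alpha and power for the primary test do not match the analysis set on which it is run, and the change log does not mention it. The original design is arithmetically sound for 105, and nothing here shows that the trial's conclusion is wrong. The ambiguity matters only near the boundary and is negligible if the true response rate is near the phase I figure.

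The 43 + 81 figures rest on three assumptions: the 17-of-43 Stage 1 rule was applied as written, all 19 extra patients fall in Stage 2, and over-enrolment did not depend on response data. The last deserves an explicit statement, because the study is open-label and the monitoring committee reviewed response data periodically during Stage 1. The p-value matter is one of labelling only. Severity: minor to should-fix.

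**What to change.** In SAP 2.7.2, 2.9 and Table 3-1, record that 124 patients were treated. State which sample and count decided the primary test and when that was set, citing the earlier analysis plan if it did so.

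If nothing was set before the data were seen, disclose that and report two results: the FAS against 53 of 124 (success probability 0.037/0.252/0.649/0.909 at true ORR 35/40/45/50%), and 45 of the first 105 treated. Note that the protocol does not define a first-105 set, and that neither that set nor the 53-of-124 boundary was pre-specified. State the three assumptions behind the 43 + 81 figures.

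Compute the UMVUE, two-stage interval and two-stage p-value with the stage sizes actually analysed, and label the SAP 4.6.4 single-stage p-value descriptive.

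The cost is wording in three SAP sections (2.7.2, 2.9 and 4.6.4), one row in Table 3-1 and one added set of operating characteristics. No new data are needed. If the earlier plan already settled the sample and count, a citation is enough for that part.
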